11.1.2 Serious Adverse Event

A serious adverse event (SAE) is any untoward medical occurrence resulting in one or more of the following:

- Results in death **NOTE:** Death due to disease progression should not be reported as a SAE, unless it is attributable by the site investigator to the study drug(s)
- Is life-threatening (defined as an event in which the subject was at risk of death at the time of the event; it does not refer to an event which hypothetically might have caused death if it were more severe)
- Requires inpatient hospitalization or prolongation of existing hospitalization
- Results in persistent or significant disability/incapacity
- Is a congenital anomaly or birth defect
- Is an important medical event (defined as a medical event(s) that may not be immediately life-threatening or result in death or hospitalization but, based upon appropriate medical and scientific judgment, may jeopardize the subject or may require intervention (e.g., medical, surgical) to prevent one of the other serious outcomes listed in the definition above). Examples of such events include, but are not limited to, intensive treatment in an emergency room or at home for allergic bronchospasm; blood dyscrasias or convulsions not resulting in hospitalization; or the development of drug dependency or drug abuse.

11.1.3 Suspected Adverse Reaction

Suspected adverse reaction means any AE for which there is a reasonable possibility that the study drug caused the adverse event. For the purposes of IND safety reporting, ‘reasonable possibility’ means there is evidence to suggest a causal relationship between the drug and the adverse event. A suspected adverse reaction implies a lesser degree of certainty about causality than adverse reaction, which means any adverse event caused by a drug.

11.1.4 Adverse Reaction

An adverse reaction means any AE caused by a drug. Adverse reactions are a subset of all suspected adverse reactions where there is reason to conclude that the drug caused the event.

11.1.5 Expected Adverse Event

Expected AEs are those events that have been previously identified as resulting from administration of the agent. For this study, an AE is considered expected when it appears in the current AE list, the Investigator’s Brochure (IB), the package insert or is included in the informed consent document as a potential risk.

11.1.6 Relatedness

AEs will be categorized according to the likelihood that they are related to the study drug(s). Specifically, they will be categorized using the following terms:

Unrelated	Adverse Event is not related to the study drug(s)
Unlikely	Adverse Event is doubtfully related to the study drug(s)
Possible	Adverse Event may be related to the study drug(s)
Probable	Adverse Event is likely related to the study drug(s)
Definite	Adverse Event is clearly related to the study drug(s)

11.2 Reporting

11.2.1 AE Reporting

- AEs will be recorded from time of signed informed consent until 30 days after discontinuation of study drug(s).
- AEs will be recorded regardless of whether or not they are considered related to the study drug(s).
- All AEs will be recorded in the subject's medical record and on the appropriate study specific eCRF form within the EDC system.
- AEs considered related to study drug(s) will be followed until resolution to \leq Grade 1 or baseline, deemed clinically insignificant, and/or until a new anti-cancer treatment starts, whichever occurs first.

11.2.2 SAE Reporting

11.2.2.1 Site Requirements for Reporting SAEs to HCRN

- SAEs will be reported from time of signed informed consent until 90 days after discontinuation of study drug(s).
- SAEs will be reported on the SAE/ECI Submission Form **within 24 hours** of discovery of the event.
- SAEs include events related and unrelated to the study drug(s).
- All SAEs will be recorded in the subject's medical record and on the appropriate study specific eCRF form within the EDC system.
- All SAEs regardless of relation to study drug will be followed until resolution to \leq Grade 1 or baseline and/or deemed clinically insignificant and/or until a new anti-cancer treatment starts, whichever occurs first.

The SAE/ECI Submission Form may be submitted to HCRN electronically to [contact]. The site investigator is responsible for informing the IRB and/or other local regulatory bodies as per local requirements.

The original copy of the SAE/ECI Submission Form and the email correspondence must be kept within the study file at the study site.

Once the SAE has resolved (see resolution guidelines listed in 11.2.1), sites must submit a follow-up SAE/ECI Submission Form within a reasonable timeframe to HCRN electronically to [contact].

11.2.2.2 HCRN Requirements for Reporting SAEs to Merck

Hoosier Cancer Research Network will report any possibly related and unexpected SAE to Merck **within one business day** of receipt of the SAE/ECI Submission Form and to regulatory authorities (FDA) per federal guidelines. Follow-up information will be provided to Merck as it is received from site.

11.3 Sponsor-Investigator Responsibilities

HCRN will send a SAE summary to the sponsor-investigator **within 1 business day** of receipt of SAE/ECI Submission Form from a site. The sponsor-investigator will promptly review the SAE summary and assess for expectedness and relatedness.

11.4 HCRN Responsibilities to FDA

HCRN will manage the Investigational New Drug Application (IND) associated with this protocol on behalf of the sponsor-investigator. HCRN will cross-reference this submission to the Merck's parent IND at the time of submission. Additionally, HCRN will submit a copy of these documents to Merck at the time of submission to FDA.

For protocols conducted under an IND, HCRN will be responsible for all communication with the FDA in accordance with 21CFR312 including but not limited to the 7 and 15 Day Reports, as well as an Annual Progress Report. Additionally, HCRN will submit a copy of these reports to Merck at the time of submission to FDA.

11.5 IND Safety Reports Unrelated to this Trial

Merck will provide to HCRN IND safety reports from external studies that involve the study drug(s) per their guidelines. HCRN will forward safety reports to the sponsor-investigator who will review these reports and determine if revisions are needed to the protocol or consent. HCRN will forward these reports to participating sites within 1 business day of receiving the sponsor-investigator's review. Based on the sponsor-investigator's review, applicable changes will be made to the protocol and informed consent document (if required). All IND safety reports will also be made available to sites via the EDC system.

Upon receipt from HCRN, site investigators (or designees) are responsible for submitting these safety reports to their respective IRBs, as per their IRB policies.

11.6 Reporting of Pregnancy and Lactation to the Sponsor-Investigator and to Merck

Although pregnancy and lactation are not considered adverse events, it is the responsibility of site investigators or their designees to report any pregnancy or lactation in a subject (spontaneously reported to them), including the pregnancy of a male subject's female partner that occurs during the trial or within 120 days of completing the trial. All subjects and female partners of male subjects who become pregnant must be followed to the completion/termination of the pregnancy. Pregnancy outcomes of spontaneous abortion, missed abortion, benign hydatidiform mole, blighted ovum, fetal death, intrauterine death, miscarriage, and stillbirth must

be reported as serious adverse events. If the pregnancy continues to term, the outcome (health of infant) must also be reported.

Such events must be reported **within 24 hours** to HCRN. HCRN will report such events to the sponsor-investigator and Merck Global Safety **within one business day** of receiving notification of the event. (Attn: Worldwide Product Safety; [contact])

11.7 Events of Clinical Interest

Events of Clinical Interest (ECI) described below must be recorded as such on the SAE/ECI Submission Form and reported **within 24 hours** to [contact] at HCRN. HCRN will report these events **within one business day** of receipt to Merck Global Safety. (Attn: Worldwide Product Safety; [contact]).

Events of clinical interest for this trial include:

1. an overdose of Funder's product that is not associated with clinical symptoms or abnormal laboratory results. For purposes of this trial, an overdose will be defined as any dose exceeding the prescribed dose for pembrolizumab greater than 10mg/kg over the prescribed dose. No specific information is available on the treatment of overdose of pembrolizumab. In the event of overdose, pembrolizumab should be discontinued and the subject should be observed closely for signs of toxicity. Appropriate supportive treatment should be provided if clinically indicated. If an adverse event(s) is associated with ("results from") the overdose of a Merck product, the adverse event(s) is reported as a serious adverse event, even if no other seriousness criteria are met.
2. an elevated AST or ALT lab value that is greater than or equal to 3X the upper limit of normal and an elevated total bilirubin lab value that is greater than or equal to 2X the upper limit of normal and, at the same time, an alkaline phosphatase lab value that is less than 2X the upper limit of normal, as determined by way of protocol-specified laboratory testing or unscheduled laboratory testing.*

***NOTE:** These criteria are based upon available regulatory guidance. The purpose of the criteria is to specify a threshold of abnormal hepatic tests that may require an additional evaluation for an underlying etiology.

12 STATISTICAL CONSIDERATION

12.1 Study design

This is a multi-institutional, randomized, placebo controlled, double-blinded phase II trial. Eligible subjects will be 1:1 randomized to placebo (Control Arm A) and pembrolizumab (Experimental Arm B). Stratification factors for randomization include: presence of visceral metastatic disease (lung, liver, or bone vs. none) at the time of initiation of first-line chemotherapy, and response to first-line chemotherapy (CR/PR vs. SD).

12.2 Definition of primary endpoint

The primary endpoint is progression-free survival (PFS), which is defined as the time from randomization to death or progression, depending on which occurs first, as per immune-related RECIST (irRECIST).

12.3 Definitions of secondary endpoints

- PFS, which is defined as the time from randomization to death or progression, depending on which occurs first as defined by RECIST 1.1.
- PFS as per irRECIST and RECIST 1.1 by PD-L1 expression levels.
- Six-month PFS rate, which is defined as the percentage of participants that are alive and progression-free, as per irRECIST and RECIST 1.1, at six months calculated from the date of randomization.
- Six-month PFS rate as per irRECIST and RECIST 1.1 by PD-L1 expression levels.
- Safety of pembrolizumab, defined as rates of Grade 1-5 toxicity according to CTCAE v4.0.
- Objective response rate (ORR) in subjects on maintenance pembrolizumab versus placebo, which is defined by irRECIST and RECIST 1.1 in subjects with measurable disease.
- ORR in subjects receiving pembrolizumab after progressing on placebo as per irRECIST and RECIST 1.1.
- Overall survival (OS), which is defined as the time from randomization to death.

12.4 Exploratory endpoints

- PFS and 6-month PFS as per irRECIST and RECIST 1.1 without visceral metastatic disease randomized to pembrolizumab versus placebo.
- Compare PD-L1 expression in primary tumor tissue and metastatic post first-line chemotherapy tumor tissue in a subgroup of subjects.
- Correlate immune infiltrates in tumor tissue with response rate, progression-free survival, and overall survival in subjects receiving pembrolizumab versus placebo
- Determine the repertoire of humoral responses and correlate with response rate, progression-free survival, and overall survival
- Determine the induction of T cell responses and correlate with response rate, progression-free survival, and overall survival
- Correlate genomic alterations with response rate, progression-free survival, and overall survival
- Correlate tobacco history with PFS in subjects receiving pembrolizumab versus placebo

12.6 Analysis plan for secondary objectives

PFS will also be compared between Arms A and B using a weighted logrank test. The weight is 0 before month 2 and 1 after month 3. The form of the weight between month 2 and 3 will take a form specified in Equation (5) of Zucker and Lakatos.⁴⁴ This weighted log-rank test is used due to its maximum efficiency. The time points (months 2 and 3) are chosen based on our belief that that treatment is likely to have minimal effect before month 2 and reach its full effect after month 3. We will also compare the PFS using the usual constant weight logrank test. PFS will also be estimated by the Kaplan-Meier method and the estimated curves will be plotted. Median PFS for both groups will be estimated and their two-sided 95% confidence intervals will be constructed.

Comparison of the 6-month PFS between the two arms will be conducted using estimates from the Kaplan-Meier method and the Greenwood formula. The resulting test is a Chi-square type of test⁴³. Subjects will be analyzed as they are randomized, regardless of the treatment that they actually receive. Data at the end of the 12-month follow-up period of the last treated patient will be used for analyses. For the placebo group, data before cross-over will be used for the analyses of primary objective. The evaluable set will be used for this analysis. PFS with respect to PD-L1 expression levels and OS will be estimated by Kaplan-Meier methods and the comparisons will be performed by logrank tests. Their medians will be estimated with 95% confidence intervals. HRs for both PFS and OS will be estimated using Cox proportional hazard models. Covariate effects will be evaluated by Cox proportional hazard models. RMST will be estimated based on the Kaplan-Meier estimates of the survival functions. ORR for pembrolizumab maintenance, placebo, and pembrolizumab after progression on placebo will be summarized by frequencies and percentages. Comparisons of rates will be performed by Pearson's chi-square tests or Fisher's exact tests. Durations of response will be summarized by median (1st, 3rd quartiles) and be compared using Wilcoxon rank sum test. These analyses will be performed using the evaluable set.

Adverse events for the safety of pembrolizumab will be summarized using frequencies and percentages with respect to grade levels. The safety set will be used for these analyses.

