6 TREATMENT DISCONTINUATION

6.1 Reasons for Discontinuing Protocol Therapy

A subject will be discontinued from protocol therapy under the following circumstances:

- If there is evidence of progressive disease. However, subjects randomized to placebo will be eligible to cross over to pembrolizumab treatment at the time of progression.
- If the site investigator thinks a change of therapy would be in the best interest of the subject.
- If the drug(s) exhibit(s) an unacceptable adverse event.
- If a subject becomes pregnant or is unwilling to use appropriate birth control techniques as outlined in the inclusion criteria.
- If there is a treatment interruption for greater than 12 weeks due to treatment related adverse event.
- Subjects can stop participating at any time. However, if they decide to stop participating in the study, subjects will continue to be followed for disease progression and survival.
- Twenty-four months of uninterrupted protocol therapy and no evidence of progressive disease.

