 - CMP will include: serum chemistries (creatinine, glucose, total protein, BUN, total CO₂, albumin, total bilirubin, alkaline phosphatase, and AST and ALT) and electrolytes (total calcium, chloride, potassium, sodium)
 - CBC (including platelets, ANC & HGB)
 - TSH, T3 and T4 tests are done on Day 1 of even numbered cycles only (i.e., Cycle 2, 4, 6, etc.). For T3 and T4, free versus total is at the site investigator's discretion
 - Correlative studies: Blood sample collection (See Table 7 above for correlative sample schedule)
- Record Adverse Events and any changes to concomitant medications
- Restaging CT or MRI of the chest, abdomen, and pelvis is performed after every four cycles of treatment (i.e., approximately every 12 weeks). Make every effort to perform the same imaging modality throughout the study.
- Pembrolizumab or placebo administration (IV)

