8.4.5 Objective response rate

The objective response rate is the proportion of all subjects with confirmed PR or CR according to RECIST, from the start of treatment until disease progression/recurrence (taking as reference for progressive disease the smallest measurements recorded since the start of treatment).

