12.10 Analysis datasets

- Enrolled set. This will comprise all subjects who meet the eligibility criteria and are registered onto the study.
- Evaluable set. This will comprise all enrolled subjects who undergo at least one post-baseline assessment or die before any evaluation.

- Safety set. This will comprise all subjects that receive at least one dose of study drug.

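### The efficacy analyses use an evaluable set defined by what happens after randomization, and the plan defines no all-randomized set

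*Combined protocol and SAP*

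**What the plan says.** Section 12.6 names the analysis population twice. After the sentences on the 6-month PFS comparison and the primary objective it says "The evaluable set will be used for this analysis". After the text on PFS by PD-L1, OS, hazard ratios, RMST, ORR and duration of response it says "These analyses will be performed using the evaluable set".

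Section 12.10 defines the evaluable set: "This will comprise all enrolled subjects who undergo at least one post-baseline assessment or die before any evaluation". Its parent, the enrolled set, is defined as "This will comprise all subjects who meet the eligibility criteria and are registered onto the study". The only other set is the safety set (at least one dose). None of the three is defined by randomization, which under section 4 comes after registration.

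Three other passages bear on the point:

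- Section 12.6, same paragraph: "Subjects will be analyzed as they are randomized, regardless of the treatment that they actually receive".
- Section 8.4.5: "The objective response rate is the proportion of all subjects with confirmed PR or CR according to RECIST". Section 12.3 limits this endpoint to subjects with measurable disease.
- Section 6.1, on subjects who stop participating: "subjects will continue to be followed for disease progression and survival". Section 7.4 schedules the survival contacts.

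**The concern.** Membership of the evaluable set is settled after randomization, and the rule treats outcomes unequally. Of two subjects who both miss every assessment, the one who dies is counted and the one who lives is not. If missed assessments are more common in one arm, that arm loses survivors and its survival looks worse than it was.

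Unequal loss is plausible here. Section 7.3.2 unblinds subjects who stop for toxicity or progression, and section 7.3.3 then lets placebo subjects cross over. Section 1.13 notes that checkpoint inhibitors became commercially available during the trial. Survival follow-up continues after treatment stops, so the plan would collect OS data on some subjects and then leave them out.

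For ORR, the unassessed leave the denominator and the rate rises. At stake is the comparability that randomization provides, across all the efficacy analyses, with no planned analysis showing how much the exclusion matters.

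**Working it through.** **1. The plan's own figures.** Section 12.5 gives: one-sided alpha 0.05, power 80%, control hazard 0.232 per month, hazard ratio 1 before month 2 and 0.462 after month 3, and censoring uniform from month 6 to month 36. Section 12.6 gives weight 0 before month 2 and 1 after month 3. I assumed a linear ramp in weight and hazard ratio between months 2 and 3, because the cited equation is not in the documents. For the weighted logrank test,

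N = (z₀.₉₅ + z₀.₈₀)² × V / D²,

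where V integrates w²·p(1−p) and D integrates w·p(1−p)·(−log HR), both over the event density. Here p is the share of the risk set in the pembrolizumab arm. The result is N = 102.3, rounded up to 103, against the stated 104. A log-linear ramp gives 101. Inflation: 104 / (1 − 4/108) = 108, so the plan allows for 4/108 = 3.7% non-evaluable. The sizing is not at fault.

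**2. Power if all 108 are analyzed.** Power = Φ(√(n × 6.183/102.3) − 1.645), where 6.183 = (1.645 + 0.842)². At n = 104 this is 80.6%. At 108 it is 81.8% if the four extra subjects carry full information, and it stays at 80.6% if they are censored at day 0. Analyzing everyone costs no power.

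**3. PFS.** A living, unassessed subject with no event would be censored at day 0 and is in no risk set when an event occurs. In a test dataset, the logrank z was −0.763 with four such subjects included and −0.763 without them. One exception is possible. Section 5.1.3.3 counts palliative radiation as progression, and the first restaging scan falls at about week 12 (section 7.2). If assessment means imaging, a real event before that scan could be lost.

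**4. OS.** The documents give no OS assumption for this design, so these inputs are assumed: no treatment effect, median OS 14 months (the figure section 1.1 gives for first-line treatment), 54 per arm, and censoring uniform over 12 to 36 months. Unassessed subjects are kept only if they die, as 12.10 requires. The hazard ratio is pembrolizumab over placebo; nominal one-sided error is 5%, and the simulated rates are good to about one percentage point.

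| Unassessed | HR (true 1.00) | One-sided error |
|---|---|---|
| 3.7% in each arm | 1.00 | 5.1% |
| 7.4% placebo only (4/54) | 0.96 | 7.3% |
| 7.4% pembrolizumab only | 1.04 | 3.4% |
| 15% placebo only | 0.92 | 9.5% |

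The shift is modest because few subjects are actually removed. The chance of being alive at censoring is (2^(−12/14) − 2^(−36/14)) / (24 × ln 2/14) = (0.552 − 0.168)/1.188 = 0.32. Of four unassessed subjects, about 4 × 0.32 = 1.3 are dropped.

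**5. ORR.** Assume that all 54 per arm have measurable disease, with 11 and 5 responders.

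- All randomized: 11/54 = 20.4% against 5/54 = 9.3%.
- Four dropped from the pembrolizumab arm: 11/50 = 22.0% against 9.3%.
- Eight and two dropped: 11/46 = 23.9% against 5/52 = 9.6%.

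The difference between arms goes from 11.1 to 12.7 to 14.3 percentage points.

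**The case against.** The strongest reply is that few subjects will be excluded. Section 7.3.1 gives every subject who ends treatment a visit with examination, laboratory tests and, if the last scan is over 28 days old, imaging. Section 7.4 continues imaging for those who stop without progression. Subjects who complete these visits are evaluable, so many early exits for toxicity stay in. The excluded would mainly be those who withdraw consent, are lost or miss visits. For the first two, little further data would exist: section 7.7 stops contact on withdrawal apart from death information. Also, 12.10 does not say that an assessment means a scan. Examination and laboratory tests are scheduled on Day 1 of every cycle, and if those count, almost nobody is excluded. All of this stands, and it limits the size of the problem. It does not supply an all-randomized set, and the undefined term leaves the choice open until the data are seen.

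Three stronger readings are tempting, and the documents do not support them.

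- A reader might infer a flat contradiction with the as-randomized sentence. Its wording concerns which arm a subject is counted in, not who is counted. The tension is with its intention-to-treat purpose. The all-subjects wording in 8.4.5 is the more direct mismatch.
- A reader might infer a clear OS bias in favour of pembrolizumab. Dropping four Arm B subjects with twice the death hazard gives an average hazard of (50×1 + 4×2)/54 = 1.074 with them in, hence 1/1.074 = 0.93 with them out. That deletes them even when they die, and 12.10 keeps those who die before any evaluation. Simulated, outright deletion gives about 0.95; keeping the deaths gives about 0.98 to 1.01.
- A reader might infer that the enrolled set removes subjects found ineligible after randomization. The text can equally be read as eligibility at registration.

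**Conclusion.** The point holds as a gap in the definition of the analysis population, of low to moderate severity. The efficacy analyses rest on a set that depends on post-randomization facts, drops living unassessed subjects while keeping those who die, and has no all-randomized counterpart.

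Primary PFS is essentially unaffected, apart from a possible non-imaging event before the first scan. For OS, if the non-evaluable share is the 3.7% the plan allows and is equal in both arms, there is no visible bias. With about 7% in one arm only, a null hazard ratio moves to roughly 0.96 to 1.04. The direction depends on which arm loses subjects and on what counts as an assessment, so the documents do not support a claim that either arm is favoured. The ORR inflation is 1.6 percentage points when four of 54 are dropped from one arm (22.0% against 20.4%). The OS and ORR sizes rest on the assumptions stated above, not on figures for this design in the documents.

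**What to change.** - In 12.10, add an all-randomized set: every randomized subject, in the arm assigned.
- In 12.6, use it for primary PFS and for OS with its hazard ratio and RMST. State that a subject with no post-baseline assessment and no event is censored at randomization for PFS and at last known alive date for OS.
- For ORR in the randomized comparison, use all randomized subjects with measurable disease at baseline, in line with 12.3, and count those without a post-baseline scan as non-responders. Without this limit, first-line complete responders with nothing to measure would enter the denominator.
- Define post-baseline assessment: imaging only, or any scheduled visit.
- Keep the evaluable set as a sensitivity analysis, and report the number excluded and the reasons by arm.

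The cost is wording. Sample size and data collection do not change, and the sizing model loses no power. ORR may read slightly lower.

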Pyrexia	10 (7)	0
Chills	9 (7)	0
Decreased appetite	6 (4)	1 (1)
Increase in aminotransferase level		
AST	13 (10)	2 (1)
ALT	11 (8)	0
Renal failure	3 (2)	2 (1)
Respiratory disorder		
Cough	11 (8)	0
Dyspnea	6 (4)	0
Pneumonitis	6 (4)	0
Skin disorder		
Rash	28 (21)	3 (2)
Pruritis	28 (21)	1 (1)
Vitiligo	12 (9)	0

Drug related adverse events occurring in at least 5 patients or drug-related grade 3 or 4 adverse events that occurred in at least 2 patients from²⁵

1.8 Inhibiting PD-1/PD-L1 signaling is associated with clinical activity in metastatic urothelial cancer.

Recently, proof of concept for targeting PD-1/PD-L1 in patients with metastatic urothelial cancer has been established. Powles et al demonstrated that in 30 patients with PD-L1-expressing (by immunohistochemistry) metastatic urothelial cancer refractory to standard chemotherapy treated with the anti-PDL1 antibody, MPDL3280A, 43% achieved an objective response.²⁶ Plimack et al reported the preliminary results of the urothelial cancer expansion cohort of KEYNOTE-012, a Phase Ib Multi-Cohort Study of MK3475 in Patients with PD-L1+ Advanced Solid Tumors. Among 33 chemotherapy-refractory patients treated with pembrolizumab 10 mg/kg every 2 weeks, 24% achieved an objective response including several durable responses.²⁷ In a phase 3 trial of pembrolizumab versus standard chemotherapy in patients with metastatic urothelial cancer progressing despite platinum-

based regimens, pembrolizumab was associated with a significant improvement in overall survival leading to approval by the US FDA for this indication.²⁸

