2.2 Secondary Objectives

- Determine the 6-month PFS as per irRECIST
- Determine the 6-month PFS as per irRECIST among the subsets of subjects with PD-L1 positive and PD-L1 negative tumors treated with pembrolizumab versus placebo.
- Determine the PFS as per irRECIST among the subsets of subjects with PD-L1 positive and PD-L1 negative tumors treated with pembrolizumab versus placebo
- Determine the PFS as per RECIST 1.1 among subjects treated with pembrolizumab versus placebo
- Determine the objective response rate (ORR) by irRECIST and RECIST 1.1 in subjects on maintenance pembrolizumab versus placebo with measurable disease
- Determine the ORR by irRECIST and RECIST 1.1 in subjects receiving pembrolizumab after progressing on placebo
- Determine overall survival (OS) in subjects treated with pembrolizumab versus placebo
- Determine the hazard ratios (HRs) with respect to both PFS and OS comparing subjects treated with pembrolizumab versus placebo
- Determine the restricted mean survival time (RMST) in subjects treated with pembrolizumab versus placebo

- Determine durations of response in subjects treated with pembrolizumab versus placebo
- Determine the safety of pembrolizumab administration in this patient population

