8.4.3 Duration of Response

Duration of overall response—the period measured from the time that measurement criteria are met for complete or partial response (whichever status is recorded first) until the date that recurrent or progressive disease is objectively documented, taking as reference the smallest measurements recorded since treatment started.

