8.5 Immune Related RECIST (irRECIST)

PFS, ORR and duration of response per irRECIST are defined as specified for the respective endpoints using RECIST 1.1 above, with the exception that a confirmation assessment of PD (4-6 weeks after the initial PD assessment) is required for subjects who remain on treatment following a documented PD per RECIST 1.1 (as detailed in section 7.6). The first date of progression, confirmed on the subsequent imaging study, will be considered the date of progression. Subjects who discontinue treatment following a documented PD assessment per RECIST 1.1 will be counted as having disease progression on the date of the documented PD assessment.

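### The between-arm Wilcoxon test of duration of response compares responders only, so it is not a randomized comparison and can mislead in either direction (minor, secondary analysis)

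*Combined protocol and SAP*

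**What the plan says.** Section 2.2 lists the objective: "Determine durations of response in subjects treated with pembrolizumab versus placebo". The analysis in section 12.6 is one sentence: "Durations of response will be summarized by median (1st, 3rd quartiles) and be compared using Wilcoxon rank sum test". That sentence does not name the groups; the objective does.

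Section 8.4.3 defines duration as "the period measured from the time that measurement criteria are met for complete or partial response", ending at documented recurrence or progression. Section 8.5 carries this over: "PFS, ORR and duration of response per irRECIST are defined as specified for the respective endpoints using RECIST 1.1 above", apart from confirmation of progression. A subject who never reaches CR or PR therefore has no duration under either criterion.

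For the analysis population, section 12.6 says "These analyses will be performed using the evaluable set". It also says that subjects are analyzed as randomized. Nothing gives non-responders a value, calls the duration comparison descriptive, or adds an analysis of time in response among all randomized subjects.

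The plan treats response itself as an outcome that may differ by arm. Section 12.3 lists "Objective response rate (ORR) in subjects on maintenance pembrolizumab versus placebo, which is defined by irRECIST and RECIST 1.1 in subjects with measurable disease", and section 12.6 compares rates by chi-square or Fisher's exact test.

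**The concern.** Randomization makes the two arms comparable. It does not make the responders in the two arms comparable, because response occurs after randomization and pembrolizumab is expected to change who responds. Under saline, the responders are subjects whose disease shrinks further without the drug. Under pembrolizumab, they may be those subjects plus others who respond only because of the drug. If the two kinds of responder have different durations, the arms differ among responders even when the drug changes nobody's duration.

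Analyzing subjects as randomized does not repair this, since the compared groups are still formed by response. Nor would replacing the Wilcoxon test with Kaplan-Meier curves and a log-rank test among responders. That would deal with responses still ongoing at the data cut, which is a separate matter.

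At stake is a p-value on a stated secondary objective. Section 13.4 requires results of all primary and secondary objectives to be posted, so it would probably be read as a treatment effect.

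**Working it through.** The plan states no response rate, duration, power or error rate for this analysis, so there is no planned figure to reproduce. The calculations below are illustrations.

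**1. Direction.** Let p0 and p1 be the response rates on placebo and pembrolizumab. Suppose the drug leaves the durations of would-be placebo responders unchanged (exponential, mean m_a) and only adds responders (exponential, mean m_b). Then

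P(placebo duration longer) = (p0/p1) × 0.5 + (1 − p0/p1) × m_a/(m_a + m_b).

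Assume p0 = 10%, p1 = 25%, m_a = 12 months, so p0/p1 = 0.4:

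| m_b (months) | Calculation | Result | Lean |
|---|---|---|---|
| 6 | 0.2 + 0.6 × 12/18 | 0.60 | placebo |
| 9 | 0.2 + 0.6 × 12/21 | 0.54 | placebo |
| 12 | 0.2 + 0.6 × 12/24 | 0.50 | none |
| 18 | 0.2 + 0.6 × 12/30 | 0.44 | pembrolizumab |

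For m_b = 6, the placebo median is 12 × ln 2 = 8.3 months. The pembrolizumab median solves 0.4·exp(−t/12) + 0.6·exp(−t/6) = 0.5, giving t = 5.4 months. Mean time in response over all subjects points the other way: 0.10 × 12 = 1.2 months on placebo and 1.2 + 0.15 × 6 = 2.1 months on pembrolizumab.

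In that case the Wilcoxon test is significant for placebo in 8.9% of simulated trials with 54 per arm, and in 85% with 1,000 per arm. The error does not shrink with sample size.

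**2. Size under a prognosis model.**

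Inputs from the documents:
- Pembrolizumab response rate 24% (section 1.8: "24% achieved an objective response including several durable responses", in 33 chemotherapy-refractory patients).
- Control hazard −ln(0.062)/12 = 0.232 per month (section 12.5), a PFS hazard applied here to duration.

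Assumptions not in the documents:
- Placebo response rate 3%, 5% or 10%.
- Standard normal prognosis g, with hazard 0.232 × exp(−0.8g).
- Response occurs when a latent variable, correlated with g, exceeds the quantile matching the response rate.

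Ratio of responder medians (pembrolizumab/placebo) when the drug changes no subject's duration, so that the correct value is 1:

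| Correlation | Placebo 3% | 5% | 10% |
|---|---|---|---|
| 0 | about 1.0 | about 1.0 | about 1.0 |
| 0.3 | 0.78 | 0.83 | 0.89 |
| 0.6 | 0.63 | 0.69 | 0.79 |

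If the design hazard ratio of 0.462 acts on duration, the true ratio is 1/0.462 = 2.16. The responder ratio is then 1.35 to 1.93 at correlations 0.3 to 0.6, and about 2.17 at zero correlation.

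**3. Numbers available.** With 52 per arm, expected responders are 0.24 × 52 = 12.5 on pembrolizumab, and 0.03 × 52 = 1.6 to 0.10 × 52 = 5.2 on placebo. These are upper figures, because response counts only in subjects with measurable disease. At 3%, the chance of no placebo responder is 0.97^52 = 0.21, and the test could not then be run.

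**4. At trial size.** Under the step 2 model with no effect on duration, correlation 0.3 to 0.6 and 52 per arm, the two-sided 5% test was significant for placebo in about 2% to 4% of simulated trials. It pointed toward placebo, significant or not, in about 54% to 64%. With the full 0.462 effect and zero correlation, it was significant for pembrolizumab in only 4% to 13%.

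**The case against.** The strongest reply concerns weight. This is a secondary analysis in a phase II trial, with no alpha or decision attached, and duration of response is missing from the endpoint list in section 12.3. Randomized comparisons of PFS, OS and response rate are already planned. With so few responders, a falsely significant result is uncommon under the step 2 model, and the scarcity of responders limits the test more than selection does. All of this stands, and it keeps the point minor.

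A second reply concerns direction. A reader might infer that the test will favor placebo, or will understate a real benefit on duration. The documents do not support that. Both outcomes require added responders to have shorter durations than those who would respond anyway, and nothing in the plan says so. Nor does it say that saline responders have the best prognosis. The background sections 1.7 and 1.8 describe PD-1 responses as long or durable, which could tilt the comparison toward pembrolizumab.

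A third reply is that the ratios depend on chosen inputs. That is correct: the lowest, 0.63, pairs the lowest placebo rate with the highest correlation, and the 24% comes from a different population. The structural point depends on none of these values.

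**Conclusion.** The point holds as a minor one. Sections 2.2, 8.4.3, 8.5 and 12.6 together plan a between-arm test in groups formed by a post-randomization outcome that treatment can change. The resulting p-value is not a randomized comparison, whichever way it leans. Its direction cannot be predicted from the documents.

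The ratios of 0.63 to 0.89 illustrate how large the distortion could be at correlations of 0.3 to 0.6; at zero correlation it disappears. They rest on an assumed placebo response rate, spread of prognosis and correlation, and on a pembrolizumab rate borrowed from chemotherapy-refractory patients. The primary PFS test is not affected.

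**What to change.** In section 12.6, delete the between-arm Wilcoxon test for duration of response. Report duration by arm among responders as descriptive only, and state that this is not a randomized comparison. The cost is one or two sentences and no new data.

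If a between-arm comparison is wanted, an optional addition is restricted mean time in response to 12 months, in all randomized subjects with measurable disease at baseline. Non-responders count as zero. The estimate is the area between the Kaplan-Meier curve for PFS and the curve for first of response, progression or death, with a bootstrap confidence interval. This takes a small amount of programming. The text should note three limits:

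- It combines response rate and duration, so the descriptive figures should stay beside it.
- With scans about every 12 weeks (84/30.4 = 2.8 months), a 12-month horizon captures only about 12 − 2.8 = 9 months of response.
- The data cut, 12 months after the last treated patient, removes administrative censoring before month 12 but not other censoring. For example, section 7.4 lets imaging stop when new treatment starts.
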